4 SELECTION AND ENROLLMENT OF PARTICIPANTS

Our target population is seniors with cognitive concerns in primary care clinics. While we anticipate that many potential participants might be attending Medicare Annual Wellness visit, we will also recruit eligible patients who will be attending the primary care clinic for other medical reasons.

4.1 Inclusion Criteria

1) Age 65 and older. **2)** Presence of cognitive concerns expressed by patient or caregiver or identified by health care providers. **3)** Registered as patient at Montefiore Medical Center and have a primary care doctor appointment that day. **4)** Able to see and hear well enough to complete intervention or control assessments. **5)** English or Spanish speaking.

4.2 Exclusion Criteria

1) Prior diagnosis of dementia or MCI as ascertained by ICD-10 codes or the presence of prescription for anti-dementia medications (cholinesterase inhibitors or Memantine) in EMR. Patients with a diagnosis containing any of the following terms will be excluded:

- a. “Dementia”
- b. “Mild Cognitive Impairment”
- c. “Alzheimer’s Disease”
- d. “Creutzfeldt-Jakob Disease”
- e. “Major Neurocognitive Disorder”
- f. “Minor Neurocognitive Disorder”

Patients with any of the following medications documented in their EMR will be excluded (generic = brand):

- a. Donepezil = Aricept
- b. Memantine = Namenda
- c. Rivastigmine = Exelon
- d. Galantamine = Razadyne
- e. Donepezil and Memantine = Namzaric

2) Adults who are permanent residents of a nursing facility.

3) Patients who do not speak English or Spanish.

4) Patients who are not seeing a primary care physician at the clinic that day.

5) Patients who are blind, deaf or cannot hear loud voice even with hearing aids.

Recruitment, enrollment, and participation of participants in this project are not limited by gender, skin color, racial/ethnic group, or economic status. We will monitor recruitment and retention patterns to ensure adequate representation of women and minorities. Since this study focuses exclusively on geriatric syndromes, it will not include children.

4.3 Study Enrollment Procedures

Potential participants may be referred by the clinic staff to the non-clinician research assistant (RA) by a message sent in the EMR, a phone call to the RA or by approaching the RA in person. Once a referral is received the RA will review the patient's electronic medical records or medical chart to determine their eligibility for participation based on the criteria above. Next, they will locate the patient within the clinic by asking the clinic staff to identify the patient.

Potential participants may also be identified by reviewing the daily clinic schedule on the electronic clinic schedule calendar. The RA will review all patients' charts that are ≥ 65 years and older with an appointment at the clinic that day to determine their eligibility based on the criteria described above. Next, they will locate the patient within the clinic by asking the clinic staff to identify the patient.

After identifying the patient referred by a clinic staff member the RA will confirm the cognitive complaint. Before offering a patient enrollment in the study, the RA will ensure that they (or their family member or friend, or a clinic staff member) have a cognitive complaint or concern about them. This information will be recorded in the database.

If the potential participant was identified by the RA from the daily schedule and determined to be eligible based on criteria from the EMR, the RA will greet the patient and say "I am X, and I am a RA. We are conducting a research study here at the clinic." The RA will give a study flyer to the potential participant and say, "Would you mind please reviewing this flyer and answering the questions on it? I will give you a few minutes, and will come back to review it with you. Do you have any questions, or problems reviewing

Flyer Questions:
 "Are you concerned about your memory?"

Yes No

"Are your loved ones concerned about your memory?"

Yes No

this flyer?” If the patient is there with family or friends, the RA can encourage the patient to let their family or friend review it with them if they are comfortable.

If the patient says or marks “Yes” to either of the questions on the flyer OR was referred to you by another source because of concerns about their memory or cognition, say, “It looks like you may be eligible for our study. We are conducting a research study to validate a new cognitive screening tool. If you are interested in participating in the study, I will ask you to complete some tasks that involve memory, health and mobility. You will receive a total of \$10 for completing the 5-minute assessment before seeing your doctor. In addition, to the 5-minute assessment before seeing your doctor, if you are interested in completing a 60-minute cognitive assessment after you see your doctor we will pay you an additional \$10. Are you interested in participating?”

Those expressing interest should be invited to come to the research office to complete the informed consent, randomization and the assessments.

COVID-19 amendment to enrollment and recruitment procedures: In response to the COVID-19 pandemic the recruitment process described above will be conducted over the telephone rather than in person. Below are descriptions of the study enrollment and recruitment procedures for the various recruitment and enrollment pathways.

Instead of the RA recruiting the participant through the flyer at the clinic waiting room, the RA will reach out to the participant over the phone on the day before their appointment to tell them about the study, screen them and conduct informed consent (see section 6.2 for details). The RA will ask the same questions as are on the flyer to potential participants over the telephone on the day before their appointment.

In a case where the patient was identified to the RA by a clinic staff member or physician, the RA will screen them for eligibility through their medical chart and if they have an appointment scheduled, they will reach out to the patient on the day before their appointment to tell them about the study, screen and conduct the verbal informed consent.

5 STUDY INTERVENTIONS

5.1 **Interventions & Administration**

Intervention arm (5-Cog): The 5-Cog battery coupled with a decision tree is a simple, 5-minute procedure that will identify older persons with cognitive impairment in primary care settings, and flag them for further evaluation. The 5-Cog battery includes the PMIS,¹ MCR diagnosis,²⁻⁴ and the paper-based Symbol Match Test. The 5-Cog battery will be given after randomization and before the patients sees the physician. After completing the 5-Cog screening, the tester will send a message through the EMR system to provide 5-Cog results and a decision tree to the treating physician. The cognitive assessment algorithm will sort patients with ‘cognitive impairment’ from those with ‘no cognitive impairment’.

Active control: Participants randomized to the active control will receive a health literacy questionnaire and grip strength assessment to match time (5 minutes), tester exposure, and gait assessment procedure in the 5-Cog arm. The Short Assessment of Health Literacy (SAHL) has comparable tests in English and Spanish, with good reliability and validity.

Participants are presented with 18 test items. For each term, a key word with related meaning and a distractor word unrelated in meaning to the test term are presented. This tests the participant's comprehension as well as pronunciation of health-related terms. The test takes 3 minutes and requires minimal training. Grip strength is measured in dominant hand with a Jamar handgrip dynamometer.⁵⁰⁻⁵² Grip strength is a validated health indicator in aging.⁵⁰⁻⁵² Low grip strength is a component of frailty definitions and predicts disability.⁵⁰⁻⁵² To parallel the study procedures and flow in the 5-Cog arm, a decision tree will be created. Results and the decision tree will be sent to the physicians through the EMR system at the same visit.

5.2 Handling of Study Interventions

The tester will obtain informed consent, prior to randomizing patients to either the 5-Cog or control interventions. We will follow the example of other pragmatic clinical trials of dementia screening in primary care clinics⁵³ by randomizing at the patient level rather than at the level of providers or clinics. This will minimize effects of unmeasured case mix differences and clinic-level clustering. As noted by Fowler et al,⁵³ the risk for "spillover" from having participating primary care clinics treat both intervention and usual-care patients is likely to be small given low levels of dementia detection.⁵⁴ The patient-based randomization should conservatively bias results in favor of usual care. [name] (Statistics Core) will computer-generate a randomized block design which will be used to assign study identification numbers and place patients into either 5-Cog or control groups.

The IRB requires us to disclose the tests to participants in both study arms; therefore, it is not feasible to blind patients. Participants and the RA who carries out the 5-Cog or health literacy and grip strength assessments are not blinded to group assignment. However, investigators, data analysts collecting outcome data of improved dementia care, and the statistician remain blinded to individual assignments.

5.3 Concomitant Interventions

5.3.1 Allowed Interventions

We will not ask physicians to deny patients any procedures offered routinely. Clinicians have access to the PMIS and other cognitive screeners in the EMR. We will not ask clinicians to avoid using these screeners in enrolled patients. But we will track cognitive screener use by clinicians in control and 5-Cog arms via the EMR.

5.3.2 Required Interventions

Not applicable

5.3.3 Prohibited Interventions

Patients with any of the following medications documented in their EMR prior to enrollment will be excluded (generic = brand):

- a. Donepezil = Aricept
- b. Memantine = Namenda
- c. Rivastigmine = Exelon
- d. Galantamine = Razadyne
- e. Donepezil and Memantine = Namzaric

5.4 Adherence Assessment

[figure not shown]
Our primary outcome is based on information from EMR on Bronx-based patients receiving primary care in our institution. This will minimize missing data issues. We will aggressively implement data management processes (supervised by the Data Core). The goals of data management are to ensure (a) data collected during the study are properly and accurately entered and documented, (b) data are stored in an electronic format that allows easy retrieval and exportation, and c) participant confidentiality. The study programmer in collaboration with the statistician manages the data. They will work with other Data and Statistical Core team members to correct identified issues and conduct quality audits of database.

We realize that not all patients will complete all of the additional tests for exploratory outcomes. However, our sample of 1,200 participants is a sufficient pool to conduct sensitivity analyses for exploratory outcomes even assuming a refusal rate of 50% for some or all of these additional tests used for secondary and exploratory outcomes.

6 STUDY PROCEDURES

6.1 Schedule of Evaluations

Figure 2. Study Flow

6.2 Description of Evaluations

6.2.1 Screening Evaluation

The RA will review all patients' charts that are ≥ 65 years and older with an appointment at the clinic on the following day to determine their eligibility based on the criteria described above. Next they will reach out to the patient over the telephone.

After identifying the eligible patients the RA will confirm that they have an appointment on the following day and describe the study to them and ask them if they would be interested in participating. If interested, the RA will confirm the cognitive complaint. Before offering a patient enrollment in the study, the RA will ensure that they (or their family member or friend, or a clinic staff member) have endorsed a cognitive complaint or expressed concern about them.

Consenting Procedure

Those with cognitive complaints, expressing interest in the study will be invited to participate at their appointment on the following day. Consent will be obtained from participants through a verbal consent process prior to enrollment. The non-clinician tester will obtain verbal consent over the telephone prior to the patient coming to the clinic for their appointment when they will also be randomized and receive the study assessments.

The consent script describes the purpose of the study, the procedures to be followed, and the risks and benefits of participation. A copy of the script can be given to each participant and this fact will be documented in the participant's record. Language in the consent form will describe data sharing. For example, *"We will store information about you in a "bank", which is a library of information from many studies. This information cannot be linked to you. In the future, researchers can apply for permission to use the information for new studies to prevent, diagnose, or treat disease. Your information may be kept for a long time, perhaps longer than 50 years. If you agree to the future use, some of your de-identified health information (not linked to you) may be placed into one or more scientific databases. These may include databases maintained by the federal government."*

6.2.2 Randomization & Assessments

Randomization

The tester will obtain informed consent, prior to randomizing patients to either the 5-Cog or control interventions. We will follow the example of other pragmatic clinical trials of dementia screening in primary care clinics⁵³ by randomizing at the patient level rather than at the level of providers or clinics. This will minimize effects of unmeasured case mix differences and clinic-level clustering. As noted by Fowler et al,⁵³ the risk for "spillover" from having participating primary care clinics treat both intervention and usual-care patients is likely to be small given low levels of dementia detection.⁵⁴ The patient-based randomization should conservatively bias results in favor of usual care.

[name] (Statistics Core) will computer-generate a randomized block design which will be used to assign study identification numbers and place patients into either 5-Cog or control groups. Patients will be stratified by gender and age (< or >75 years). Briefly, an encrypted file containing the group assignment is prepared for each study identification number. The file is stored in RedCap the database program used for this trial. The assignments are presented to the RA in sequential order at the time the participant is enrolled, following the eligibility assessment, and administer the indicated screen. Participants and the RA who administers the tests are not blinded to group assignment. However, investigators, data analysts collecting outcome data, and the statistician remain blinded to individual assignments.

Assessments

Intervention arm (5-Cog): This simple, 5-minute procedure will identify older persons with cognitive impairment in primary care settings, and flag them for further evaluation. The 5-Cog battery includes the PMIS, MCR diagnosis,⁶⁻⁸ and the paper-based Symbol Match test. Our cognitive assessment algorithm will sort patients with or at high risk of developing ‘cognitive impairment’ from those with ‘no cognitive impairment’. Moreover, it is coupled with a decision tree to guide clinicians through the necessary steps to follow up on 5-Cog results. Because primary care clinicians and staff may not have the time to complete even a 5-minute screen,^{12, 15, 16} non-clinicians (RAs) will administer the 5-Cog and communicate the results to primary care physicians for further action.

Active control: Participants randomized to the active control will receive a health literacy questionnaire and grip strength assessment to match the time (~5 minutes), tester exposure, and gait assessment procedure in the 5-Cog arm. The SAHL has comparable tests in English (SAHL-E) and Spanish (SAHL-S), with good reliability and validity in both languages. Participants are presented with 18 test items. For each term, a key word with related meaning and a distractor word unrelated in meaning to the test term is presented. This tests the participant’s comprehension as well as pronunciation of health-related terms. The test takes 3 minutes to complete and requires minimal training. Grip strength is measured in dominant hand with a Jamar handgrip dynamometer.⁵⁰⁻⁵² Grip strength is a validated health indicator in aging.⁵⁰⁻⁵² Low grip strength is a component of frailty definitions and predicts disability.⁵⁰⁻⁵² To parallel the study procedures and flow in the 5-Cog arm, a decision tree will be created. Results and the decision tree will be presented to the physicians at the same visit.

Additional Assessments: In order to avoid interrupting the normal clinic flow, these additional assessments, which will be used as covariates or exploratory outcomes in our analyses, will be done following the clinician’s assessment of the patient. These exploratory measures will help us generate and test new hypothesis and provide insights into the effects of the 5-Cog battery. We realize that not all patients will be able to complete part or all of the tests due to other commitments. Nonetheless, our overall sample size of 1,200 participants provides a sufficient pool assuming a non-completion rate of 50%.

- a. Patient characteristics: Demographic, socio-economic status and medical illness

burden.

- b. Neuropsychological battery – due to safety concerns with in person visits, as of July 27th, 2020 participants will be offered the opportunity to complete the neuropsychological evaluation over the phone or via video conference.

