Recruitment: We will enroll 1,200 older patients with cognitive concerns (reported by patient or noted by caregivers or clinic staff) over 30 months; estimated enrollment rate is 8-10 per week. This enrollment rate conservatively assumes a >50% refusal rate from potentially eligible participants. Our enrollment rate in our pilot study at the same clinical site was about 6-8 per week when participants were asked to complete a longer battery of assessments. While we anticipate that many potential participants may be attending our primary care clinics for their Medicare Annual Wellness visit,¹² we will also recruit patients attending the clinics for other medical reasons. Montefiore Medical Center is the main healthcare system for Bronx county; one of the most ethnically diverse communities in the nation with an elderly population of 140,000 (U.S. census data). Patients age 65 and older account for >20,000 primary care visits at Montefiore annually; ensuring an adequate pool for recruitment. The non-clinician tester will approach all patients age 65 and over attending our primary care clinic sites. Those expressing interest will be screened at the same visit to determine eligibility. Information regarding demographics, socio-economic status and medical illnesses will be collected.

Primary Outcome: Our primary outcome is **improved dementia care**. This outcome is collected prospectively from EMR and related medical records by data analysts (blinded to study arm allocation and test results), and do not require patient interviews. This primary outcome is defined as meeting any one of the following endpoints within 90 days of the clinic visit at which the patient was randomized. Similar composite endpoints to define

Figure 1. 5-Cog Flow & Decision Tree

dementia care have been used in several prior clinical trials in cognitively impaired patients.³²⁻³⁶

1. New diagnosis of dementia (relevant ICD-10 codes) or MCI (331.83) documented in the EMR. The recent DSM-V criteria³⁷ include categories of ‘major neurocognitive disorder’ and ‘mild neurocognitive disorder,’ which overlap with dementia and MCI. These categories will also be included but a recent internal audit indicated that they are as yet not in widespread use in our primary care clinics (cf. specialty clinics).

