9.2 Sample Size and Randomization

This randomized study has 600 subjects for each of the 2 groups. Assuming a non-completion rate of EMR entries of 10% over 90 days and that 25%, 30% or 35% of control subjects will experience ‘improved dementia care,’ we can detect odds ratios of 1.46, 1.43 or 1.42, respectively, on the effect of 5-Cog on improving dementia care with 80% power using a two-sided test with significance level of 0.05. There is a paucity of studies examining efficacy of brief cognitive screens in primary care. One non-randomized trial of

screening by medical assistants coupled with a decision tree in primary care clinics showed new physician action in 17% of patients with a positive screen in intervention sites compared to 1% in control sites.³⁶ Action included new dementia diagnosis, referral to specialist or initiating dementia treatment (similar to our primary outcome). While our projected effect size used for sample size estimation is conservatively lower than that reported in this previous study,³⁶ the effect size from this previous study was not used to calculate power given its preliminary, non-randomized nature but is presented in support of our assumptions. A review of 8 studies of detection of mild dementia in primary care showed that sensitivity ranged from 9% to 41%.⁵⁵ Detection rates in clinics are even lower for earlier dementia stages such as MCI.⁵⁶ These observations support our assumptions of lower rates of improved dementia care in our control group.

Cohort retention: This is not a major issue for this RCT as primary outcomes are based on clinical encounters information collected from EMR and other administrative data sources in patients residing in Bronx County and receiving primary care in our institution. Also, primary outcomes do not require repeat in-person testing after baseline assessments.

- *Non-completion:* We realize that not all patients will complete the additional tests described above as covariates or exploratory outcomes. We will complete as many of the tests as possible depending on patients' availability. Nonetheless, our overall sample size of 1,200 participants provides a sufficient pool to conduct sensitivity analyses assuming non-completion rate of 50%.

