9.5 Data Analyses

We will examine data for potential outliers and analyze the robustness of our findings

against them. We will perform per-protocol analysis to assess the sensitivity of our findings to protocol deviations. Furthermore, the impact of baseline imbalance will be determined by comparing the analysis outcomes with and without controlling for baseline attributes. Chi-square test will be used to compare ‘improved dementia care’ outcome within 90 days post-intervention between the intervention and control groups. Logistic regression model adjusted for covariates will also be used. We will use **intention to treat analysis**.⁵⁷ Pre-specified baseline covariates to account for **confounders** in the planned analysis include age, gender, education, and chronic illnesses. Baseline distribution of covariates will be compared to assess adequacy of randomization. We do not discount residual/unmeasured confounding – though this is more of an issue in observational studies without randomization. We will report adjusted and crude estimates of associations to assess confounding, and discuss limitations of the study.

Primary outcome: Chi-square test will be used to compare ‘improved dementia care’ outcome within 90 days post-intervention between the intervention and control groups. Logistic model adjusted for covariates will also be used.

Heterogeneity of treatment effect (HTE) is the nonrandom, explainable variability in the direction and magnitude of treatment effects for individuals within a population. The main goals of HTE analysis are to estimate treatment effects in clinically relevant subgroups and to predict whether an individual might benefit from a treatment. In this RCT, we will specifically address HTE due to gender (male/female), ethnicity (African-American/Hispanic/Caucasian) and education (less than high school/ high school graduate). Treatment effects in these subgroups will be evaluated using stratified analysis. Alternative, an interaction term between the subgroup characteristic and treatment group will also be tested.

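### Covariates that section 9.5 calls baseline are scheduled in section 6.2.2 after the physician visit, in a block with 50% assumed non-completion; the supporting adjusted and subgroup analyses are exposed, the primary chi-square test is not

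*Combined protocol and SAP*

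**What the plan says.** Section 9.5 compares the primary outcome between arms with a chi-square test under intention to treat. A covariate-adjusted logistic model is used as well, and crude and adjusted estimates are both reported. The pre-specified baseline covariates "in the planned analysis include age, gender, education, and chronic illnesses". The same section compares the baseline distribution of covariates to judge whether randomization worked, repeats the analysis with and without baseline attributes, and examines treatment effects by gender, ethnicity and education.

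Section 6.2.2 says when those variables are collected. Its Additional Assessments, "which will be used as covariates or exploratory outcomes in our analyses, will be done following the clinician" has seen the patient, begin with "a. Patient characteristics: Demographic, socio-economic status and medical illness" burden. The paragraph accepts that some patients will not complete part or all of the block because of other commitments, and regards the sample as sufficient at 50% non-completion. Section 9.2 repeats the allowance and again mentions covariates: "not all patients will complete the additional tests described above as covariates or exploratory outcomes".

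Section 3, under Recruitment, says: "Information regarding demographics, socio-economic status and medical illnesses will be collected". The sentence follows the one on eligibility screening but gives no time relative to randomization.

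**The concern.** A baseline covariate should be fixed before randomization and known for essentially everyone randomized. On the schedule in section 6.2.2, education and illness burden are recorded after the arm has been assigned, after the result has gone to the physician, and after same-visit orders and referrals. Two problems can follow.

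- **Missing data.** Whether a patient stays for the extra block may depend on the visit, for example on an abnormal result, a referral or a trip to the laboratory. Participants and research assistants know the arm. If completion depends on arm and outcome, an adjusted model restricted to completers no longer follows intention to treat. A gap between crude and adjusted estimates could then reflect selection, although section 9.5 reads that gap as a measure of baseline imbalance. The comparison of arms at baseline has the same weakness.
- **Changed values.** Illness burden taken after the visit could include conditions first recorded because of the screen. This does not apply to education or ethnicity, which a same-day screen cannot change.

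**Working it through.** **Timing.** Sections 5.1 and 6.2.2 give the order as consent, randomization, 5-Cog or control assessment, physician visit, Additional Assessments. Sections 4.3 and 6.2.1 describe the pre-visit contact in detail (chart review, confirmation of the cognitive concern, telephone consent) and do not include collection of education or illness burden. Section 6.2.2 is therefore the only place that schedules these variables, and section 3 does not override it. Age and gender are stratification factors, so two of the four covariates are known at randomization. Education and ethnicity are not named in 6.2.2; they are read into demographics and socio-economic status. The plan gives no source (interview or EMR) for chronic illnesses and no rule for missing covariates.

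**The plan's own power figure.** Inputs from section 9.2: "This randomized study has 600 subjects for each of the 2 groups"; "Assuming a non-completion rate of EMR entries of 10% over 90 days", so 600 × 0.90 = 540 per arm; "25%, 30% or 35% of control subjects will experience" the outcome; detectable odds ratios (OR) 1.46, 1.43 and 1.42; 80% power; two-sided 0.05.

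With control rate p1, the intervention rate is p2 = OR·p1/(1 − p1 + OR·p1). With m = (p1 + p2)/2,

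power = Φ{ [ |p2 − p1|·√n − 1.96·√(2m(1 − m)) ] / √( p1(1 − p1) + p2(1 − p2) ) }.

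For p1 = 0.25 and OR = 1.46: p2 = 0.3274 and m = 0.2887. At n = 540 the argument is (1.798 − 1.96 × 0.6408)/0.6385 = 0.848, so power is 80.2%. The other two scenarios give 79.3% and 80.2%. Solving for 80% power gives ORs of 1.459, 1.434 and 1.419. The stated figures reproduce with a two-proportion test that uses no covariates.

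**Illustration for a complete-case adjusted model.** Two assumptions are needed that the plan does not state: patients without covariates are dropped, and the full 50% applies to education or illness burden. The two-proportion formula stands in for the logistic model.

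| Patients per arm | Power at the stated ORs | Detectable ORs (control 25% / 30% / 35%) |
|---|---|---|
| 540 (plan) | 80.2% / 79.3% / 80.2% | 1.46 / 1.43 / 1.42 |
| 300 (50% of 600) | 55.2% / 54.3% / 55.2% | 1.65 / 1.62 / 1.60 |
| 270 (50% of 540) | 50.9% / 50.1% / 50.9% | 1.69 / 1.66 / 1.64 |

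The true rate for these items is unknown, so here is the range. With covariates missing in 10%, 20%, 30% or 40% of the 540, power at the stated ORs is about 75-76%, 70-71%, 64-65% or 58%.

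**Illustration of selection.** Among completers, observed OR = true OR × (c11/c10)/(c01/c00), where c is the completion rate by arm (first index, 1 = 5-Cog) and outcome (second index, 1 = improved dementia care). Assume 50% completion in every cell except 5-Cog patients with the outcome, and a true OR of 1.46:

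- 45% in that cell: 1.46 × 0.45/0.50 = 1.31
- 40%: 1.46 × 0.40/0.50 = 1.17
- 55%: 1.46 × 0.55/0.50 = 1.61

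These rates are chosen to show the mechanism. The documents give no completion rate by arm or outcome.

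**The case against.** The strongest reply is that the trial's main result does not use these data. That is correct. A reader might infer from the 50-51% figure that the trial is underpowered, or that its primary analysis rests on post-intervention covariates. The documents do not support either reading: the logistic model is additional, and the stated power belongs to the chi-square test.

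A second reply is that the timing is unclear rather than wrong, since section 3 mentions the data under Recruitment and section 9.5 calls them baseline. This stands in part. The sponsor may intend early collection, but no procedure section provides for it, and staff following 6.2.2 would collect the data late.

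A third is that the 50% is mainly about the 60-minute neuropsychological battery. Section 5.4 ties the allowance to tests for secondary and exploratory outcomes, and section 4.3 offers the long assessment as a separately paid option. This largely stands. Sections 6.2.2 and 9.2 do mention covariates when they make the allowance, but a few demographic questions would probably be missed far less often.

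Finally, a reader might infer that the covariates will be selectively missing. The plan attributes non-completion to other commitments and reports nothing by arm. Selective missingness is a risk created by the schedule, not something the documents show.

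**Conclusion.** The point holds as an inconsistency with consequences for supporting analyses. Section 6.2.2 schedules demographics, socio-economic status and illness burden after the intervention; section 9.5 needs education and chronic illnesses as baseline values; section 3 does not settle the matter. The adjusted model, the imbalance check, the baseline comparison and the education and ethnicity subgroups are exposed. For education and ethnicity the risk is missingness only; for illness burden the recorded value may also be affected.

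The size cannot be fixed from the documents. The fall to 50-51% power, with detectable ORs of 1.69, 1.66 and 1.64, is an extreme illustration that requires complete-case analysis and the full 50% allowance in addition to the 10% EMR loss. The change is worth making because it is cheap and keeps the adjusted and crude estimates on the same patients.

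**What to change.** - **Section 6.2.2:** move item (a), patient characteristics, out of the post-visit block. Ask education and ethnicity at the telephone screening and consent contact that already precedes randomization. Take chronic illnesses from EMR entries dated before the randomization visit. Only the neuropsychological battery then stays after the visit.
- **Section 9.5:** state that the unadjusted chi-square test is primary; that covariates and subgroup variables use pre-randomization values only; and that the adjusted model keeps every patient in the chi-square analysis, with a simple stated rule for covariate values still missing (for example, imputation done without reference to arm). Early collection reduces missing values but does not remove the need for such a rule.
- **Sections 3 and 9.2:** align with the above. Section 3 should say that the information is collected before randomization, and the 50% allowance in 9.2 should no longer refer to covariates.

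The cost is a short protocol edit and one or two minutes of questions in an existing contact, with no extra visit or staff. The trade-off is that the illness measure becomes EMR-based and depends on how completely conditions were coded before the visit.
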